5.1.2 Exclusion criteria

Patients who meet the following criteria at the time of screening will be excluded (from CORRECT Trial):

Phase II Study of Perindopril and Regorafenib in mCRC (PARICCA)

- Patients with hypotension (less than 90/60mm Hg) or at risk of symptomatic hypotension (fainting or dizziness) will be excluded.
- Prior treatment with regorafenib or any VEGFR-targeting kinase inhibitor.
- Previous assignment to treatment during this study. Patients permanently withdrawn from study participation will not be allowed to re-enter the study.
- Concurrent cancer requiring treatment that is distinct in primary site or histology from colorectal cancer.
- Major surgical procedure, open biopsy, or significant traumatic injury within 28 days before start of study medication.
- Unstable/uncontrolled cardiac disease including: congestive heart failure \geq New York Heart Association (NYHA) class 2; unstable angina (angina symptoms at rest), new-onset angina (begun within the last 3 months); myocardial infarction less than 6 months before start of study drug; cardiac arrhythmias requiring anti-arrhythmic therapy (beta blockers or digoxin are permitted).
- Uncontrolled hypertension. (Systolic blood pressure $>$ 150 mmHg or diastolic pressure $>$ 90 mmHg despite optimal medical management).
- Patients with pheochromocytoma.
- Arterial or venous thrombotic or embolic events such as cerebrovascular accident (including transient ischemic attacks), deep vein thrombosis or pulmonary embolism within the 6 months before start of study medication.
- Ongoing infection $>$ grade 2 NCI-CTCAE version 4.03
- Known history of human immunodeficiency virus (HIV) infection.
- Known history of chronic hepatitis B or C.
- Patients with seizure disorder requiring medication.
- Symptomatic metastatic brain or meningeal tumors unless the patient is $>$ 6 months from definitive therapy, has a negative imaging study within 4 weeks of study entry and is clinically stable with respect to the tumor at the time of study entry. Also the patient must not be undergoing acute steroid therapy or taper (chronic steroid therapy is acceptable provided that the dose is stable for one month prior to and following screening radiographic studies)
- History of organ allograft
- Patients with evidence or history of bleeding diathesis, including patients who have had a transfusion and/or radiographic endoscopic or elective operative intervention to control the bleeding or hemorrhage event within four weeks prior to the study.
- Non-healing wound, ulcer, or bone fracture.
- Renal impairment or failure requiring hemo-or peritoneal dialysis.
- Patients with severe hepatic impairment.
- Dehydration NCI-CTC version 4.03 grade $>$ 1.
- Substance abuse, medical, psychological or social conditions that may interfere with the patient's participation in the study or evaluation of the study results

Phase II Study of Perindopril and Regorafenib in mCRC (PARICCA)

- Any illness or medical conditions that are unstable or could jeopardize the safety of the study
- Interstitial lung disease with ongoing signs and symptoms at the time of informed consent.
- Persistent proteinuria of CTC Grade 3 or higher. Quantification of proteinuria done by urinary protein/creatinine ratio on a random urine sample preferably taken at mid-morning. If protein/creatinine ratio is greater than 30g/mol Creat, then a 24-hour urine protein test should be performed to confirm Grade 3 or higher proteinuria (> 3.5 g/24 hours).
- Patients unable to swallow oral medications
- Any malabsorption condition
- Unresolved toxicity higher than NCI-CTCAE (version 4.03) Grade 1 attributed to any prior therapy/procedure excluding alopecia and oxaliplatin induced neurotoxicity ≤Grade 2
- Patients who are hypersensitive to perindopril, as well as those hypersensitive to regorafenib, sorafenib, drugs in the same class or any ingredient in the formulation.
- Patients who cannot tolerate the full dose of perindopril (4 mg) for any reason.
- Patients receiving systemic anticancer therapy including cytotoxic therapy, signal transduction inhibitors, immunotherapy, hormonal therapy and experimental or approved therapies during this trial or within 14 days before starting to receive study medication.

In addition, patients will be excluded for the following reasons (From perindopril monograph). Patients with a history of hereditary/idiopathic angioedema, or angioedema related to previous treatment with an angiotensin converting enzyme inhibitor.

- Pregnant women or those planning to become pregnant, nursing women.
- Patients with hereditary problems of galactose intolerance, glucose-galactose malabsorption, or the Lapp lactase deficiency.
- Patients with pre-existing anti-hypertension treatment with an ACE inhibitor or angiotensin receptor blocker (ARB) are to be excluded. Co-administration of ACE inhibitors, including COVERSYL®, with other agents blocking the Renin-Angiotensin System (RAS), such as ARBs or aliskiren-containing drugs, will not be allowed, since such treatment has been associated with an increased incidence of severe hypotension, renal failure, and hyperkalemia.

5.1.3 Justification of selection criteria

The exclusion of certain concomitant conditions and medications as outlined above and in Section 6.9 was necessitated by the known toxicity profile of the agents under investigation and its interaction with other classes of medications, and also based on the understanding of the concomitant conditions in colorectal cancer. This is to assure, to the best of our ability, the safety of the patients who would participate in this study.

5.2 Withdrawal of subjects from study

Patients will remain on trial and will receive regorafenib and perindopril until clinical radiological disease progression, based on RECIST v1.1 criteria. If patients progress on regorafenib, both drugs will be stopped. However, after the patient progresses (i.e. is no longer on trial) the medication can be continued if the investigator feels that there is a clinical benefit.

A subject may discontinue participation in this study at any time at the investigator's discretion or at the request of the subject.

If a subject discontinues before treatment starts (Cycle 1, day 1) she/he is not required to complete end of study assessments.

If a subject discontinues after receiving treatment for any reason, the investigator should make every effort to complete end of study assessment and the one month follow-up assessments of concomitant medications and adverse events.

Any occurrence of death, and any excluded medications taken after study withdrawal should be documented in the CRF and source documents.

Subjects withdrawn from the study retain their subject number, if already given. New subjects will be allocated a new subject number.

5.2.1 Withdrawal of subjects from study treatment

Subjects *must* be withdrawn from study treatment for the following reasons:

- At their own request or at the request of their legally acceptable representative.
- At any time during study treatment and without giving reasons, a subject may decline to participate further. The subject will not suffer any disadvantage as a result.
- If, in the investigator's opinion, continuation of study treatment would be harmful to the subject's well-being.
- Severe allergic reactions, such as exfoliate erythroderma, anaphylaxis, or vascular collapse.
- Any other potential adverse reaction deemed sufficiently serious to warrant discontinuation of treatment by the Investigator.
- Substantial non-compliance with study procedures.
- Patients with a b-HCG test consistent with pregnancy. Pregnancy will be reported along the same timelines as a serious adverse event (see Section 7.5.2).
- Use of illicit drugs or other substances that may, in the opinion of the Investigator or a designated associate(s), have a reasonable chance of contributing to toxicity or otherwise confound the results.
- Any hemorrhage or bleeding event > CTCAE Grade 3 within 4 weeks of start of study medication.

Phase II Study of Perindopril and Regorafenib in mCRC (PARICCA)

- Development of any intercurrent illness or situation which would, in the judgment of the Investigator, may affect assessments of clinical status and study endpoints to a relevant degree.
- Patients should come off study treatment for disease progression. If the treating physician feels that the patient will receive clinical benefit from continued study treatment despite progression, the patient may remain on study drug. However, the patient will be considered as having progressive disease, as per the RECIST criteria, version 1.1.
- The development of a second malignancy.
- Patient lost to follow up.
- Interruption of study drug is longer than 28 consecutive days (including the 1 week break in each cycle).
- More than two dose reductions of the study drug are necessary.
- Death.

A subject who is terminated from the study after signing the informed consent but before starting the drug is regarded as a “screening failure”.

Any subject removed from study treatment will remain under medical supervision until discharge or transfer is medically acceptable.

In all cases, the reason for withdrawal must be recorded in the CRF and in the subject's medical records.

Details for the premature termination of the study are provided in Section 10 (Premature termination of the study).

For all subjects who discontinue study treatment, relevant visit data will be entered into the case report form and any unused study drug will be accounted for and returned. Adverse events or clinical laboratory abnormalities that cause a patient to discontinue from study treatment should be followed until they recover or stabilized.

All subjects will enter the follow-up period upon discontinuation of the treatment drugs. Regardless of the reason for discontinuation all subjects will be followed for survival until death is documented, except for those who specifically withdraw consent to follow-up. Subjects who withdraw consent from study drug treatment may enter the Follow-up Period.

Assessment of survival status will be performed approximately every month. In addition, for subjects, who discontinue study treatment and have not experienced PD, available tumor assessments will be recorded in the CRF until PD is documented.

Phase II Study of Perindopril and Regorafenib in mCRC (PARICCA)

Death due to mCRC is not a serious adverse event. If any patient should die during the study treatment or within 30 days of their last dose of study drug, of causes NOT related to the disease itself (mCRC), the Investigator or a designated associate(s) will inform the Bayer HealthCare Medical hotline. If the cause of death is not related to the disease itself (mCRC), the cause of death should be recorded in detail within 24 hours of notification to the investigator on a Serious Adverse Event Form and transmitted to Health Canada.

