6.4.2 Regorafenib

Regorafenib will be administered 160 mg daily for 21 days of a 28-day cycle. Regorafenib will be administered with low fat breakfast, one hour after perindopril. A low fat breakfast as defined by the monograph¹⁰ is one that is <30% fat, ~300-550 calories (see appendix 14.4).

The rationale for the dose in this study is based upon the phase I data from Study 11650 (in which escalating doses from 10 mg to 220 mg of regorafenib were administered on a discontinuous schedule [3 weeks out of every 4]) and same dose and schedule have been used in Study 14387 (including Asian subjects).

Signs of anti-tumor activity were observed in subjects receiving doses from 60 mg up to 220 mg per day on a discontinuous schedule (3 weeks out of every 4). However, of the 220 mg/day cohort, 8 out of 12 subjects required a dose reduction for toxicity, whereas only 1 subject of 12 on the 160 mg/day cohort required such a dose reduction. Thus, based upon the efficacy and toxicity data, 160 mg was chosen as the dose for this study.

Dose administration

Regorafenib will be orally administered. The Investigator or designated study personnel is responsible for dispensing the study drug to patients.

Regorafenib should be taken in the morning with approximately 8 fluid ounces (240 mL) of water. The study drug should be administered after a light (<30% fat) breakfast. Some examples of low-fat breakfasts are provided in Appendix 14.4.

If a dose of regorafenib is missed, the subsequent dose of regorafenib should not be doubled. The investigator should be informed if the dose of regorafenib taken exceeded the scheduled dose.

Dose modification and delays

(Note that this confidential information comes from Bayer's CONCUR study protocol (integrated protocol v2.0, dated 28Dec2012).

Phase II Study of Perindopril and Regorafenib in mCRC (PARICCA)

Doses of study drug may be delayed or reduced in case of clinically significant hematologic and other toxicities that are possibly, probably or definitely related to protocol therapy.

Toxicities will be graded using the NCI Common Terminology Criteria Version 4.2.

The modifications of regorafenib will follow the following pre-defined dose levels:

Table 2: dose modifications for regorafenib

Dose level 0 (standard dose)	160 mg po od	4 tablets of regorafenib, 40 mg-tablet,
Dose level -1	120 mg po od	3 tablets of regorafenib, 40 mg-tablet,
Dose level -2	80 mg po od	2 tablets of regorafenib, 40 mg-tablet,

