If a subject experiences several toxicities and there are conflicting recommendations, the recommended dose adjustment which reduces the dose to the lowest level should be used.

Table 3 outlines dose adjustments for toxicities related to study drug except hand-foot skin reaction, hypertension and liver function test (ALT and AST) abnormalities. **Table 4** outlines the suggested dose reductions for HFSR while **Table 5** outlines suggested dose reductions for treatment-emergent hypertension. **Table 6** outlines the suggested dose reductions for ALT and/or AST increases related to study drug.

If reduction by more than two dose levels is required, treatment will be discontinued.

If a dose reduction has been performed, intra- subject dose re-escalation can be considered (up to the maximal 160 mg daily dose) at the discretion of the treating physician provided that the toxicity (ies) has resolved to baseline.

Table 3: Dose Modification/Delay for Toxicities Related to Study Drug (Except Hand Foot Skin Reaction, Hypertension, AST and ALT)^a

Grade of Event (CTCAE version 4.03)	Dose Interruption	Dose Modification	Dose for Subsequent Cycles
Grade 0-2	Treat on time	No change	No change

Phase II Study of Perindopril and Regorafenib in mCRC (PARICCA)

Grade 3	Delay until \leq Grade 2 ^b	Reduce 1 dose level	If toxicity remains \leq Grade 2, dose re-escalation can be considered at the discretion of the treating investigator. If dose is re-escalated and toxicity (\geq Grade 3) recurs, institute permanent dose reduction.
Grade 4	Delay until \leq Grade 2 ^b	Reduce by 1 dose level. Permanent discontinuation can be considered at treating investigator's discretion.	

a Excludes alopecia, non-refractory nausea/vomiting, non-refractory hypersensitivity, non clinical significant and asymptomatic laboratory abnormalities.

b If no recovery after a 4-week delay, treatment will be permanently discontinued.

In addition to these recommended dose modifications, subjects who develop diarrhea, mucositis, anorexia or other events predisposing to fluid loss or inadequate fluid intake should be carefully monitored and rehydrated as clinically necessary. This is in order to minimize the risk of postural hypotension and renal failure.

Skin Toxicity Grade (according to CTCAE version 4.03 "Palmar-plantar erythrodysesthesia syndrome")	Occurrence c	Suggested Dose Modification c

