Grade 3	Systolic BP ≥ 160 mmHg or diastolic BP ≥ 100 mmHg OR More than one drug or more intensive therapy than previously used indicated	Treat with the aim to achieve diastolic BP ≤ 90 mmHg -Start anti-hypertensive medication AND/OR -Increase current anti-hypertensive medication AND/OR -Add additional anti-hypertensive medications.	Hold regorafenib until diastolic BP ≤ 90 mmHg, and if symptomatic, until symptoms resolved. When regorafenib is restarted, continue at the same dose level. If BP is not controlled with the addition of new or more intensive therapy, reduce by 1 dose level ^b . If Grade 3 hypertension recurs despite dose reduction and antihypertensive therapy, reduce another dose level ^c .
Grade 4	Life-threatening consequences (e.g. malignant hypertension, transient or permanent neurologic deficit, hypertensive crisis)		Discontinue therapy

Abbreviations: BP = blood pressure; CTCAE = Common Terminology Criteria for Adverse Events, version 4.03
 
a Subjects requiring a delay of > 4 weeks should discontinue protocol therapy.
 
b If blood pressure remains controlled for at least one full cycle, dose re-escalation is permitted at the investigator's discretion.
 
c Subjects requiring > 2 dose reductions (a dose lower than 80 mg po od) should discontinue protocol therapy.
			

Phase II Study of Perindopril and Regorafenib in mCRC (PARICCA)

Blood pressure (BP) should be monitored weekly for the first 6 weeks of treatment. Blood pressure is to be recorded by qualified staff, e.g. a study nurse, treating physician, or nurse practitioner and entered onto the CRF.

The dose modification schedule for treatment emergent hypertension during regorafenib dosing should be followed (see Table 5). Subjects' BP measurements will be monitored and appropriate treatment to effectively control hypertension under regorafenib treatment is strongly recommended.

The selection of anti-hypertensive medication used in this setting should be performed at the investigator's discretion, considering possible site-specific treatment guidelines. All medication should be recorded in the subject's CRF.

Phase II Study of Perindopril and Regorafenib in mCRC (PARICCA)

Table 6: Dose modifications/interruption for ALT and/or AST increases related to study drug			
Grade of Event (CTCAE version 4.03)	1 st occurrence	Restart	Reoccurrence

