AST and/or ALT baseline G0 → G1 or baseline G1 → G2	Treat on time and check AST, ALT and bilirubin 2x/week for 2 weeks followed by weekly assessments for at least 4 weeks.		Treat on time and check AST, ALT and bilirubin 2x/week for 2 weeks followed by weekly assessments for at least 4 weeks.
AST and/or ALT baseline G0 → G2	Delay until ≤ G1 and check AST, ALT, bilirubin 2x/week.	Reduce 1 dose level and check AST, ALT, bilirubin 2x/week for 2 weeks followed by weekly assessments for at least 4 weeks. ^a	Discontinue ^b
AST and/or ALT baseline any grade → G3	Delay until ≤ G1 if baseline was G0 or G1 OR until G2 if baseline was G2. Check AST, ALT, bilirubin 2x/week. If ALT or AST > 8 x ULN with a concomitant rise in bilirubin (of any degree) compared to previous bilirubin values, consider permanent discontinuation at the first occurrence ^b .	Reduce 1 dose level and check AST, ALT, bilirubin 2x/week for 2 weeks followed by weekly assessments for at least 4 weeks. ^a	Discontinue ^b
AST and/or ALT baseline any grade → G4	Discontinue ^b		

Abbreviations: AST = aspartate aminotransferase, ALT = alanine aminotransferase
 
^a If all values remain stable for 2 full cycles, dose re-escalation may be considered at the discretion of the investigator. After re-escalation AST, ALT, bilirubin should be checked 2x/week for 2 weeks, followed by weekly assessments for at least 4 weeks.
 
^b In case of discontinuation, check AST, ALT, bilirubin should be checked twice a week for 2 weeks, followed by weekly assessments until recovery to baseline.
			

During the first 2 cycles of treatment, ALT, AST and bilirubin must be monitored weekly.

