Regorafenib has been associated with an increased incidence of electrolyte abnormalities (including hypophosphatemia, hypocalcemia, hyponatremia and hypokalemia) and metabolic abnormalities (including increases in thyroid stimulating hormone, lipase and amylase). The abnormalities are generally of mild to moderate severity, not associated with clinical manifestations, and do not usually require dose interruptions or reductions. It is recommended to monitor biochemical and metabolic parameters during regorafenib treatment and to institute appropriate replacement therapy according to standard clinical practice if required. Dose interruption or reduction, or permanent discontinuation of regorafenib should be considered in case of persistent or recurrent significant abnormalities.

Since drugs with anti-angiogenic properties may suppress wound healing, treatment with regorafenib should be stopped at least 2 weeks prior to scheduled surgery. The decision to resume regorafenib after surgery should be based on clinical judgment of adequate wound healing. Regorafenib should be discontinued in patients with wound dehiscence.

Regorafenib may decrease heart rate. Caution should be observed in patients with a low heart rate at baseline (< 60 beats per minute), a history of syncope or arrhythmia, sick sinus syndrome, sinoatrial block, atrioventricular (AV) block, ischemic heart disease, or congestive heart failure.

Patients with a history of ischemic heart disease should be monitored for clinical signs and symptoms of myocardial ischemia. In patients who develop new or acute onset cardiac ischemia and/or infarction regorafenib should be withheld until resolution. The decision to re-initiate regorafenib therapy should be based on careful consideration of the potential benefits and risks of the individual patient. Regorafenib should be permanently discontinued if there is no resolution.

Phase II Study of Perindopril and Regorafenib in mCRC (PARICCA)

Regorafenib should be permanently discontinued in patients who develop gastrointestinal perforation or fistula.

Treatment with regorafenib should be stopped in patients with severe or life threatening hemorrhage. Patients receiving warfarin should be closely monitored.

For patients with observed worsening of liver function tests, dose modification (interruption, reduction) or discontinuation of regorafenib is recommended.

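### For a drug-related grade 4 bleed after week 4, the compulsory withdrawal rule in 5.2.1 has lapsed and Table 3 defaults to a reduced-dose restart, while 7.5 says to stop regorafenib: a low-severity inconsistency between safety rules

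*Combined protocol and SAP*

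**What the plan says.** Section 5.2.1 lists events for which withdrawal from study treatment is compulsory. Its only bleeding entry is "Any hemorrhage or bleeding event > CTCAE Grade 3 within 4 weeks of start of study medication". No reason is given for the time limit.

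Section 6.4.2 governs regorafenib dose changes and opens permissively: "Doses of study drug may be delayed or reduced in case of clinically significant hematologic and other toxicities". Table 3 covers every drug-related toxicity except hand-foot skin reaction (HFSR), hypertension and AST/ALT. A footnote narrows it further: "Excludes alopecia, non-refractory nausea/vomiting, non-refractory hypersensitivity, non clinical significant and asymptomatic laboratory abnormalities". Bleeding is in neither list of exceptions. At grade 4 the table calls for a delay until grade 2 or lower, and then "Reduce by 1 dose level. Permanent discontinuation can be considered at treating"; the sentence ends by leaving that choice to the investigator's discretion. Permanent discontinuation is compulsory only if there is no recovery after a 4-week delay. Once the toxicity is back to baseline, 6.4.2 lets the physician raise the dose again, up to 160 mg.

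Section 7.5, in text introduced as coming from the regorafenib monograph, says: "Treatment with regorafenib should be stopped in patients with severe or life threatening hemorrhage". It sets no time limit and does not mention restarting.

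**The concern.** The three texts give different default actions for the same patient, and the protocol does not say which prevails. Section 6.1 refers to 5.2 for ending treatment and to 6.4 for dose changes; it does not mention 7.5. A clinician following that route after week 4 reaches Table 3 and its reduced-dose restart without being directed to the hemorrhage instruction.

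What is at stake is re-exposure after a life-threatening bleed. The section on expected adverse events names hemorrhage among the most serious regorafenib reactions and, with hypertension, as one of the two most often seen of these. The point concerns patient safety and dosing only.

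**Working it through.** The plan gives no figure to reproduce here, so the check is a trace through the text. Take a patient with a drug-related grade 4 bleed in cycle 2 that recovers to grade 2 or lower, with a total interruption of no more than 28 days.

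| Text | Does it apply? | Instruction | Restart |
|---|---|---|---|
| 5.2.1, bleeding entry | No: outside the 4-week limit | None | Not addressed |
| 5.2.1, interruption over 28 consecutive days | No, by construction of the case | None | Not addressed |
| 6.4.2, Table 3, grade 4 row | Yes: drug-related and not exempted | Delay, then reduce one level | Default is to restart; permanent stop optional |
| 7.5, hemorrhage sentence | Yes: grade 4 is life-threatening (7.5.1.2.2) | Stop regorafenib | No provision to resume |

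Four checks on the trace:

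1. *Grade sign in 5.2.1.* Grade 4 meets the threshold whether the sign is read as above grade 3 or as at or above grade 3. Only the time limit takes this patient out of the rule.
2. *Origin of the time limit.* The exclusion criteria in 5.1.2 use a four-week look-back for bleeding that needed intervention, so the limit may have been carried over from there. That is inference, and on either reading a bleed after week 4 is not covered.
3. *Rule for conflicting recommendations.* Section 6.4.2 says to take the lowest dose when recommendations conflict, but this is written for a subject with several toxicities. It does not address one event treated differently in two sections.
4. *Meaning of 'stopped' in 7.5.* Where that section intends a pause, it says so: a decision to resume after surgery, withholding until resolution for cardiac ischemia, and discontinuing until investigation has excluded lung disease for unexplained respiratory symptoms. The hemorrhage sentence has no such clause, so its natural meaning is that treatment ends. The word is still weaker than the explicit permanent discontinuation that 7.5 uses for perforation or fistula.

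The time limit leaves much of the treatment period uncovered. Share of treatment time after day 28:

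- 2 cycles (Table 7, lower end): 1 − 28/56 = 0.50
- 4 cycles (Table 7, upper end): 1 − 28/112 = 0.75
- four months on trial (1.6), at 30.4 days a month: 1 − 28/121.6 = 0.77
- CORRECT median PFS of 1.9 months (1.6), 57.8 days: 1 − 28/57.8 = 0.52

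These are shares of time on treatment. They do not measure bleeding risk, and the documents give no bleeding rate that would convert them.

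**The case against.** The strongest reply is that the texts can be followed together. Permanent discontinuation is one of Table 3's two options, and 6.4.2 is permissive throughout. An investigator who stops for good therefore complies with 5.2.1, Table 3 and 7.5. This stands. A reader might infer a flat contradiction, or that the protocol obliges a restart; the documents support neither. What remains is a default in Table 3 that differs from the instruction in 7.5.

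Several stopping rules without a time limit also remain. Section 4 lists unacceptable toxicity as a reason for treatment to end. Section 5.2 allows discontinuation at any time at the investigator's discretion. Section 5.2.1 requires withdrawal when the investigator thinks continuing would be harmful or the reaction is serious enough. A life-threatening bleed is a serious adverse event reportable within 24 hours, clinically significant bleeding is of special safety interest, and the trial has one centre, so practice cannot diverge between sites. These points stand and keep the severity low. They rest on judgement or on reporting, however, and do not restore the compulsory rule that the sponsor chose for the first four weeks.

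A reader might also take Tables 5 and 6 as proof that Table 3 is wrong, since grade 4 hypertension and "AST and/or ALT baseline any grade → G4" both lead to discontinuation. That goes too far. Those are event-specific rules, and a general table that leaves grade 4 events to judgement is an ordinary design choice.

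**Conclusion.** The inconsistency is real but narrow. It arises only for a drug-related grade 4 bleed, more than 4 weeks after starting drug, that recovers in time and whose investigator chooses to restart. Probably very few patients meet all of these conditions; that is a judgement, because the documents give no bleeding rate. The shares of 50% to 77% might be read as the size of the problem, but they describe exposure time only.

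The conclusion assumes that the 7.5 sentence is meant as a working instruction, although it is presented as monograph text, and that its wording most naturally means treatment ends. If the sponsor meant a temporary halt, Table 3 and 7.5 would agree on allowing a restart, and the protocol should say so.

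The primary HFSR comparison and the sample size are unaffected. Severity is low. The change is worth making because a few words alter the default action after a life-threatening event.

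**What to change.** Align 5.2.1 and Table 3 with 7.5:

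1. In 5.2.1, remove the 4-week limit from the bleeding entry, so that a grade 4 bleed at any time on study treatment requires withdrawal.
2. Add grade 4 hemorrhage to the Table 3 exceptions, with a cross-reference to 5.2.1 and 7.5.
3. In 7.5, write that regorafenib is permanently discontinued for life threatening hemorrhage. Have the sponsor's clinicians state separately there whether restart is allowed after a severe (grade 3) bleed. The present sentence covers both severities with one verb, so without this the same conflict with Table 3 would remain at grade 3.

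The cost is a few wording changes in one protocol amendment, with no change to visits, sample size or analysis. The clinical downside is that an occasional patient who could have restarted at a lower dose comes off drug. Preferring a permanent stop to a supervised restart is a clinical choice, and the sponsor should confirm it.
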